## 7.10 Safety Assessments

All safety and tolerability variables will be listed and summarised descriptively or frequency tables where appropriate on the SAF. No imputation will be made in case of missing values.

### 7.10.1 Adverse Events

Adverse events (AEs) will be assigned to a period based on the start date. ADRs are defined as AEs that determined to have a “Reasonable Possibility” of causal relationship to the study drug.

Duration of the AE and time to the AE occurrence from start of study drug or victim drug will be calculated and presented in days and time.

AE Occurrence from Start of Study Drug or Victim Drug = Date/Time of Onset- Start Date/Time of Administration. If Time is Missing, Date of Onset - Date of Administration +1. Duration of AE = Date/Time of Resolution - Date/Time of Onset. If Time is Missing, Date of Resolution - Date of Onset +1. The following summaries of AEs will be presented.

- Overall summary of AEs.
- Summary of AEs by SOC and PT.
- Summary of ADRs by SOC, PT
- Summary of AEs by SOC, PT by maximum severity

The frequency and incidence of AEs will be summarised by System Organ Class (SOC) and Preferred Term (PT) by cohort, group and treatment. The summary will be sorted by International Agreed Order for SOC and alphabetical order for PT (or by frequency from the highest to the lowest).

For summaries of AEs multiple occurrences of the same event within a subject will be counted once in the summaries by SOC and PT; multiple occurrences of the same event within a subject will be counted once in the maximum intensity category (severe > moderate > mild) and/or maximum drug relationship category (reasonable possibility > no reasonable possibility). If intensity or relationship is found to be missing the most severe occurrence will be imputed for that particular summary.

Treatment periods for adverse events are as followed.

① Group 1

Visit	Treatment
Day 1 ~ Day 4	Rosuvastatin alone
Day 4 ~ Day 5	Sildenafil alone
Day 6 ~ Day 8	Edaravone alone
Day 9 ~ Day 11	Rosuvastatin + Edaravone
Day 12 ~ Day 20 including end of study assessment	Sildenafil + Edaravone

② Group 2

Visit	Treatment
Day 1 ~ Day 2	Furosemide alone
Day 3 ~ Day 5	Edaravone alone
Day 6 ~ Day 14 including end of study assessment	Furosemide+ Edaravone

③ Japanese in Group 3, Group 4 and Group 5

Visit in Group 3	Visit in Group 4	Visit in Group 5	Treatment
Day 1 ~ Day 3	Day 7 ~ Day 9 including end of study assessment	Day 4 ~ Day 6	Fasted
Day 4 ~ Day 6	Day 1 ~ Day 3	Day 7 ~ Day 9 including end of study assessment	Before meal
Day 7 ~ Day 9 including end of study assessment	Day 4 ~ Day 6	Day 1 ~ Day 3	After meal

④ Caucasian in Group 3, Group 4 and Group 5

Visit in Group 3	Visit in Group 4	Visit in Group 5	Treatment
Day 1 ~ Day 8 including end of study assessment	Day 4 ~ Day 11 including end of study assessment	Day 7 ~ Day 14 including end of study assessment	Fasted

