9.2.5.2 Adverse events

An adverse event (AE) is any untoward medical occurrence or unintended sign (including an abnormal laboratory finding), symptoms, and disease in a patient or subject who is administered the study drug or victim drugs during safety evaluation period, and which does not necessarily need to have a causal relationship with the treatment.

The investigator (or subinvestigator) will assess AEs that occur in the subjects from the start of study drug or victim drug administration to the end-of-study assessment and record the results in the CRF.

(1) Symptoms and diseases

The investigator (or subinvestigator) will assess whether any AE has occurred in the subjects based on the interview and physical examination.

(2) Objective findings

The investigator (or subinvestigator) will identify any clinically significant abnormal finding* and handle it as an AE.

* “Clinically significant abnormal findings” will be identified according to the following criteria.

- If a clinical sign or symptom is related to the abnormal findings.
If these symptoms or signs are reported as AEs, the related abnormal laboratory findings will not be reported as separate AEs.
- If any internal or surgical treatment is given to the subject for the laboratory abnormality.

- If the study drug dosing regimen is changed due to the laboratory abnormality (e.g., dose change, or an interruption or discontinuation of the study drug).
- If the investigator (or subinvestigator) judges the abnormality as clinically significant for other reason(s).

(3) Assessments and criteria of AEs

1) Date of onset

The date of onset is defined as the date when symptoms are detected or the date when a laboratory test is performed for laboratory abnormalities. In this study, the onset time will also be recorded for all AEs occurring during hospitalization.

2) Severity

The severity of AEs will be classified as shown below.

- (1) Mild: The event does not interfere with activities of daily living.
- (2) Moderate: The event interferes to some extent with activities of daily living.
- (3) Severe: The event interferes significantly with activities of daily living.

3) Seriousness

The seriousness of AEs will be classified as shown below.

1. Not serious: AEs not meeting the criteria listed in 2.
2. Serious: A serious AE (SAE) meets any of the following, from a) to g).
 - a) Death
 - b) A case which may lead to death

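### SAP 7.10.1 assigns adverse events to treatment by calendar start date although onset time is recorded, so pre-dose events on switch days are counted under the treatment that starts later that morning

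*SAP*

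**What the plan says.** **Assignment rule.** SAP 7.10.1: "Adverse events (AEs) will be assigned to a period based on the start date". Tables of treatment periods in whole days follow. In Group 1 they include "Day 1 ~ Day 4 Rosuvastatin alone", "Day 4 ~ Day 5 Sildenafil alone" and "Day 6 ~ Day 8 Edaravone alone", then Days 9 to 11 for rosuvastatin + edaravone and Days 12 to 20 for sildenafil + edaravone. In Group 2 the rows are Days 1 to 2 (furosemide alone), 3 to 5 (edaravone alone) and 6 to 14 (furosemide + edaravone).

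**Use of the assignment.** Frequency and incidence are summarised "by System Organ Class (SOC) and Preferred Term (PT) by cohort, group and treatment".

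**Onset time is collected.** Protocol 9.2.5.2: "In this study, the onset time will also be recorded for all AEs occurring during hospitalization". The SAP already uses it for another variable: "AE Occurrence from Start of Study Drug or Victim Drug = Date/Time of Onset- Start Date/Time of Administration".

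**How onset is dated.** Protocol 9.2.5.2: "The date of onset is defined as the date when symptoms are detected". For laboratory abnormalities it is the date of the test.

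**Dose times.** The schedules (Protocol 9.1, SAP 2.3) put time zero at 08:00, except in the Cohort 2 condition of dosing 4 hours after a meal, where it is 11:00.

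**The concern.** Treatment changes at the dose, but the rows change at midnight. Everything with onset between midnight and the dose on a switch day moves from the treatment the subject was on to the one about to be given.

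This can happen in routine conduct. Vital signs and a 12-lead ECG are scheduled before the dose on the Cohort 1 switch days (Protocol 9.2.5.1). A symptom detected at such a check takes that day's date.

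The sensory tests show the inconsistency best. They are done before the dose on Group 1 Day 6 and Group 2 Day 3, and SAP section 6 makes those values the baseline. Numbness found at that check and reported as an AE with that onset date would be both a pre-edaravone baseline finding and an event under edaravone alone.

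Cohort 1's primary objective includes safety and tolerability under coadministration, so AE incidence by treatment is a main safety output. The misassignment runs from one treatment into the treatment it will be read against.

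**Working it through.** The plan states no figure for this, so there is nothing to reproduce. The check lists each switch day, its dose time and the SAP row it falls in, and computes:

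pre-dose share = hours from midnight to the dose ÷ (days in the new row × 24).

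**Cohort 1 (dose at 08:00)**

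| Group, day | SAP row for that day | Row length | Pre-dose share | Already taken by then? |
|---|---|---|---|---|
| 1, Day 4 | rosuvastatin alone and sildenafil alone | – | undetermined | no sildenafil yet |
| 1, Day 6 | edaravone alone | 3 × 24 = 72 h | 8/72 = 11.1% | no edaravone yet |
| 1, Day 9 | rosuvastatin + edaravone | 72 h | 8/72 = 11.1% | both, but not together |
| 1, Day 12 | sildenafil + edaravone | 9 × 24 = 216 h | 8/216 = 3.7% | both, but not together |
| 2, Day 3 | edaravone alone | 72 h | 8/72 = 11.1% | no edaravone yet |
| 2, Day 6 | furosemide + edaravone | 216 h | 8/216 = 3.7% | both, but not together |

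**Loss from the preceding treatment.** Furosemide alone runs dose to dose from Day 1 08:00 to Day 3 08:00, which is 48 h. Its row stops at the end of Day 2, after 40 h, so it loses 8/48 = 16.7%. Sildenafil alone (Day 4 08:00 to Day 6 08:00) also loses its last 8 of 48 h.

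**Cohort 2, Japanese subjects.** There are six switches: Days 4 and 7 in Groups 3, 4 and 5. Edaravone is given in every period and only the meal condition changes.
- Day 4: 8/72 = 11.1% in Groups 3 and 4; 11/72 = 15.3% in Group 5, where the design has the 11:00 dose.
- Day 7: the row includes the end-of-study assessment. Run to Day 14 it is 8 × 24 = 192 h, giving 11/192 = 5.7% in Group 3 (11:00 dose) and 8/192 = 4.2% in Groups 4 and 5.

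Caucasian subjects have one period and no switch.

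**The Group 4 and 5 rows.** The design gives Group 4 as after meal, fasted, before meal; the SAP rows give before meal, after meal, fasted. The design gives Group 5 as before meal, after meal, fasted; the SAP rows give after meal, fasted, before meal. All six labels disagree. As printed, the Group 4 shift happens to give pre-dose events on Days 4 and 7 the label of the condition just completed. The date-rule error in Group 4 therefore appears once those labels are corrected.

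**Is onset time available?** Every switch day is an in-patient day (Protocol 8.6.1: Day -1 to Day 15 in Group 1, to Day 9 in Group 2 and for Japanese Cohort 2 subjects). Onset time should therefore be on record.

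**Internal check.** An event at 03:00 on Group 1 Day 6 falls in the edaravone-alone row, yet its onset relative to the first edaravone dose is 03:00 − 08:00 = −5 h.

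**The case against.** **Scope.** A reader might infer that on every switch day events are counted under a drug not yet given. The documents do not support that. Of 12 group-by-day switches it is clearly true for two (Group 1 Day 6, Group 2 Day 3). Group 1 Day 4 would be a third only if the overlap were settled in favour of sildenafil. On the other Cohort 1 switch days both drugs have been taken before, and what has not been given is the combination dose. All Cohort 2 switches, including both at 11:00, are from edaravone to edaravone.

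**Size.** Shares of hours are not shares of events. As an illustration, take the earlier oral study's 21 of 74 subjects with AEs (Protocol section 1), one event each, spread evenly over the study:
- Group 1: 32 × 21/74 = 9.1 events; four switch mornings give 32 h of 456 h (19 × 24), so 9.1 × 32/456 = 0.6. Without Day 4, 9.1 × 24/456 = 0.5.
- Group 2: 34 × 21/74 = 9.6 events; 16 h of 312 h (13 × 24), so 9.6 × 16/312 = 0.5.

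That is about one event in Cohort 1, or about two if the rate doubles. No laboratory draw is scheduled on a switch day, and vital-sign or ECG findings count only if clinically significant. This stands, with one reservation: dating onset by detection at a pre-dose check could concentrate events in those hours.

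**Safeguards.** The investigator weighs timing when judging causality, and all data are listed. This limits harm to the adverse drug reaction tables but does not correct the all-AE incidence tables.

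**Unseen text.** SAP 7.2 (Data Handling) was not in the text available for this review, and SAP 7.1 mentions rules added at data review. A supplementary rule cannot be excluded, but it cannot be assumed to override an explicit sentence in 7.10.1.

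**Conclusion.** The point holds. The date rule misplaces pre-dose events on switch days although the time needed to place them is collected. The error is plainest on Group 1 Day 6 and Group 2 Day 3. On Group 1 Days 9 and 12 and Group 2 Day 6 the event goes to a combination dose not yet given. In Japanese Cohort 2 subjects it goes to the next meal condition: in Group 3 as the rows stand, and in Groups 4 and 5 once their rows match the design. The rows do not settle Group 1 Day 4.

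In Cohort 1, between 3.7% and 11.1% of a row's hours precede its first dose. These figures assume scheduled dose times and rows ending on the nominal end-of-study day.

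The consequence is confined to descriptive AE tables and is probably small. The pharmacokinetic conclusions are untouched. The mislabelled Group 4 and 5 rows in the same section are the larger defect, because they misplace whole periods, but correcting them would not remove this one.

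**What to change.** Replace the assignment sentence in SAP 7.10.1 with a rule to this effect:

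*Each AE is assigned to the treatment most recently started at its onset date and time: at or after the actual date and time of that treatment's first dose, and before the first dose of the next treatment. The last treatment extends to the end-of-study assessment. Only if onset time is missing is the start date used; an event on a switch day is then assigned to the treatment starting that day.*

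In the same edit, reconcile the Day 4 overlap in Group 1 and the Group 4 and 5 rows with the design.

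**Effect.** The pre-dose hours return to the preceding treatment. Furosemide alone regains its full 48 h. Edaravone alone still spans 72 h, but from dose to dose. Day 4 events with a recorded time are settled.

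**Cost.** A short text change and a different merge condition, with no new data. Onset time need not be recorded after discharge, but no switch occurs then. The small downside is that events with a missing time keep the present ambiguity. If the database is already locked, Protocol 13.5 requires the change and its reason in a revised SAP and the study report, with results before and after it shown separately.

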8.4 Duration of Dosing

(1) Cohort 1

1) Group 1

Edaravone suspension: Multiple doses (Day 6 to Day 13)
Rosuvastatin tablets: Single dose (Day 1 and Day 9)
Sildenafil: Single dose (Day 4 and Day 12)

2) Group 2

Edaravone suspension: Multiple doses (Day 3 to Day 7)

Furosemide tablets: Single dose (Day 1 and Day 6)

(2) Cohort 2

Edaravone suspension: Single dose (Day 1, Day 4, and Day 7)

[Rationales for setting]

(1) Cohort 1

For evaluation of effects on sildenafil in Group 1, a dose period has been set at that required to assess CYP3A induction by edaravone.

The edaravone dose period has been set in consideration of time points when steady states of edaravone and its metabolites will be reached for effect evaluation of rosuvastatin in Group 1 and for Group 2. The victim drugs will be administered in a single-dose manner, which is adequate for the assessment of their pharmacokinetics and changes in plasma concentrations. An adequate dose interval between rosuvastatin and sildenafil has been set in consideration of their elimination rates for Group 1.

(2) Cohort 2

The study drug will be administered in a single-dose manner, which is adequate to evaluate meal effects.

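### SAP 7.10.1 puts Day 4 in two Group 1 adverse event columns, and sets 2 days of sildenafil or furosemide alone against a nominal 9 days in combination

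*SAP*

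**What the plan says.** SAP 7.10.1 gives the allocation rule: "Adverse events (AEs) will be assigned to a period based on the start date". It then plans the tables: "The frequency and incidence of AEs will be summarised by System Organ Class (SOC) and Preferred Term (PT) by cohort, group and treatment".

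For Group 1, the first two windows are "Day 1 ~ Day 4 Rosuvastatin alone" and "Day 4 ~ Day 5 Sildenafil alone". Edaravone alone follows on Day 6 to 8, then rosuvastatin with edaravone on Day 9 to 11, and last "Day 12 ~ Day 20 including end of study assessment Sildenafil + Edaravone".

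For Group 2, the windows are "Day 1 ~ Day 2 Furosemide alone", then edaravone alone on Day 3 to 5, then "Day 6 ~ Day 14 including end of study assessment Furosemide+ Edaravone".

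Protocol 8.4 gives the dosing days: "Sildenafil: Single dose (Day 4 and Day 12"), with edaravone on Day 6 to 13 in Group 1. In Group 2, furosemide is given on Day 1 and Day 6, and edaravone on Day 3 to 7. The end-of-study assessment is 7 ± 2 days after the last dose of study drug (SAP 2.2.1).

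**The concern.** The start-date rule cannot place an event that starts on Day 4 in Group 1, because two windows claim that date. Such an event could be counted twice, or placed differently by different programmers. Day 4 matters because it is the day sildenafil is given alone. If it is read as rosuvastatin, the sildenafil-alone column is left with Day 5 only.

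The second problem is the length of the windows. Incidence means subjects with at least one event, so it rises with the number of days observed even if no drug does anything. The final combination columns absorb the whole post-dosing follow-up, and the alone columns have no counterpart to it. A reader comparing sildenafil alone with sildenafil plus edaravone, or furosemide alone with furosemide plus edaravone, would expect to see more events in combination for that reason alone. Safety and tolerability of the victim drugs on coadministration belong to the Cohort 1 primary objective (SAP 3.1), and this is the table that sets the conditions side by side.

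**Working it through.** **Counting dates.** Each window is last day − first day + 1.

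| Group | Column | Days | Dates |
|---|---|---|---|
| 1 | Rosuvastatin alone | 1–4 | 4 |
| 1 | Sildenafil alone | 4–5 | 2 |
| 1 | Edaravone alone | 6–8 | 3 |
| 1 | Rosuvastatin + edaravone | 9–11 | 3 |
| 1 | Sildenafil + edaravone | 12–20 | 9 |
| 2 | Furosemide alone | 1–2 | 2 |
| 2 | Edaravone alone | 3–5 | 3 |
| 2 | Furosemide + edaravone | 6–14 | 9 |

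Group 1 sums to 21 dates over a 20-day span, and the extra date is Day 4. Group 2 sums to 14 over 14 days. No other boundary overlaps and no date is missing.

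**The plan's end days.** Last edaravone dose plus 7 gives 13 + 7 = Day 20 and 7 + 7 = Day 14, as the SAP states. With the ±2-day visit window, the combination columns run 7, 9 or 11 days. Of these, 5, 7 or 9 follow the last edaravone dose.

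**Scheduled checks per window** (Protocol 9.2.5.1):
- Laboratory tests: 1 alone (Day 5; Day 2 in Group 2) against 2 in combination (Day 14 and end of study; Day 8 and end of study).
- Vital-sign and ECG time points: 4 + 2 = 6 alone (Day 4–5) against 4 + 2 + 1 + 1 + 1 = 9 in combination (Days 12, 13, 14, 15 and end of study). Group 2 has the same counts.

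**Expected incidence with no drug effect.** The documents give no daily risk, so I assume h = 1% to 5% per day. Incidence over d days is 1 − (1 − h)^d.

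| | h = 1% | h = 5% |
|---|---|---|
| Alone, 2 days | 1.99% | 9.75% |
| Combination, 9 days | 8.65% | 36.98% |
| Ratio, 9 v 2 days | 4.3 | 3.8 |
| Ratio, 7 v 2 days | 3.4 | 3.1 |
| Ratio, 11 v 2 days | 5.3 | 4.4 |

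Expected subjects with an event, 2 v 9 days:
- Group 1 (n = 32): 0.6 v 2.8 at 1%, and 3.1 v 11.8 at 5%.
- Group 2 (n = 34): 0.7 v 2.9 at 1%, and 3.3 v 12.6 at 5%.

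**Lower late risk.** Suppose the risk falls to f × h after Day 14 (Group 1) or Day 8 (Group 2). For a combination window of D days the ratio is [1 − (1 − h)^3 (1 − f h)^(D−3)] / [1 − (1 − h)^2].
- f = 0.5: 2.5 to 2.3 (D = 7), 2.9 to 2.7 (D = 9), 3.4 to 3.1 (D = 11).
- f = 0: 1.49 to 1.46 for every D.

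**Day 4.** Expected Day 4 onsets are 32 × h = 0.3 to 1.6 subjects. If Day 4 went to rosuvastatin, the sildenafil comparison would be 9 v 1 day (ratio 8.6 to 7.4) and the rosuvastatin comparison 3 v 4 days (0.75 to 0.77).

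**The case against.** On Day 4, the protocol places that day in Period II throughout, including the measurements before sildenafil. The SAP speaks of assigning events to a period, so the Day 4 in the rosuvastatin row looks like a slip for Day 3. That is probably right, and it supports the correction. It also makes the 9 v 1 day reading unlikely. SAP 7.1 mentions data handling rules added at the data review meeting, and I have seen neither those rules nor the text of SAP 7.2. A Day 4 rule might stand there, but the table in 7.10.1 would still contradict itself.

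On window length, carrying post-dosing events in the last condition is the SAP's convention in every group, and it keeps delayed events with the combination. Protocol 9.2.5.2 names a dosing period and a 7-day Period (1), but as two parts of one assessment period. It does not ask for separate tabulation. Part of the imbalance comes from the design: edaravone starts on Day 6 or Day 3, so the alone windows cannot be lengthened to match. All of this stands, but it does not make the columns comparable.

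There are real mitigations. No test or decision rule uses the table. Time to onset and listings let a reader find late events. Laboratory, vital-sign and ECG values are summarised by scheduled visit or time point, so they are unaffected. The summary of adverse drug reactions draws on the investigator's causality judgement, but it is given no separate windows.

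Finally, the size depends on late risk. Only one visit follows discharge on Day 15 or Day 9, so detected risk may well fall. With no late risk, the present ratio equals the one left after a Day 14/Day 8 cut-off (1.49 to 1.46), and that split gains nothing.

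**Conclusion.** Both parts hold. The Day 4 overlap is an error in the allocation rule, with an expected 0.3 to 1.6 of 32 subjects affected at the assumed risks. The 2-day against nominal 9-day comparison is a presentation weakness that makes the combination look worse. With no drug effect, the nominal 9-day incidence ratio is 4.3 to 3.8 under constant risk, 2.9 to 2.7 if late risk is halved, and about 1.5 if late risk is zero. Across the 7- to 11-day windows and all three late-risk cases, the range is about 1.5 to 5.3.

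These ratios rest on an assumed 1% to 5% daily risk, which the documents do not give. The day counts and scheduled-test counts come directly from the documents. Because the table is descriptive, this is a worthwhile improvement rather than a threat to the study's conclusions. The Day 4 correction is the part that should not be left as it is.

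**What to change.** In SAP 7.10.1:

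1. Make the Group 1 windows non-overlapping: rosuvastatin alone Day 1–3, sildenafil alone Day 4–5. Rosuvastatin is then 3 v 3 days.
2. Split each final combination window into an on-treatment and a follow-up column, and keep the current total beside them.
3. Print the days observed in each column header, with the actual range for follow-up.
4. State the cut-off and its trade-off:
   - *Option A:* on-treatment Day 12–14 (Group 1) and Day 6–8 (Group 2). This gives 3 v 2 days, 1 v 1 laboratory tests and 7 v 6 vital-sign and ECG time points, but keeps one undosed day. The constant-risk ratio is 1.49 to 1.46.
   - *Option B:* on-treatment Day 12–13 and Day 6–7. This gives 2 v 2 days, 6 v 6 time points and a ratio of 1.0, but no laboratory test falls in the combination column.
   - I suggest Option A. Protocol 9.2.5.2 dates a laboratory event by the day of the test, so under Option B none found at a scheduled test could appear in the combination column.
5. Add a footnote that the combination always comes last, so order remains confounded with treatment under either option.

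No new data or case report form field is needed, since onset date, and onset time in hospital, are already recorded. The cost is window wording, one follow-up column per group beside the current total, and header text. The columns will hold fewer events, and Option A leaves 3 v 2 days.

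The SAP is at its final Ver2.0 and the data review meeting has been held, so this is a documented change under Protocol 13.5. Before data lock, the change and its reason go in the SAP and study report. After lock, a revised SAP is needed and results are shown separately for before and after the change. The documents do not show whether lock has occurred.
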